AIM 2: To conduct iterative usability testing on an evolving prototype of a new tool, “PERK”. This will involve both qualitative and quantitative assessments of ease of use of “PERK”. We will perform “think aloud” and “near live” testing to develop a prototype that will be revised and evaluated.

AIM 3: To evaluate the feasibility, acceptability and preliminary efficacy on provider adoption of a new tool compared to the current tool, in a pilot trial. We will conduct a 6 month pre-post analysis of “PERK” by comparing it to retrospective data from the first 6 months of PE CALC. Our primary feasibility outcome is post-pilot provider satisfaction. Secondary outcomes include stakeholder acceptability.

***H1:** PERK will demonstrate higher rates of provider satisfaction as compared to PE CALC.* Our primary efficacy outcome is increased provider adoption. Secondary outcomes include increased CTPA yield [% of positive tests], and decreased CTPA ordering. ***H2:** “PERK” will demonstrate higher provider adoption as compared to PE CALC.*

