6. RECRUITMENT METHODS

- *Describe the source of potential subjects*
- *Describe the methods that will be used to identify potential subjects*
- *Describe any materials that will be used to recruit subjects. A copy of any advertisements (flyers, radio scripts, etc.) should be submitted along with the protocol.*
- *If monetary compensation is to be offered, this should be indicated in the protocol*

Eligible subjects for all three aims of this study will be medical doctors and physician assistants working full time at NSUH or LIJMC. This includes residents in the Emergency Medicine/Internal Medicine program.

For AIM 1, potential subjects will be identified using the Electronic Medical Records (EMR) based on PE CALC use. We will contact participants via our secure email system. We will inform participants about the study, offering a \$50 reimbursement for their time.

In addition, we will contact department heads at NSUH and LIJMC, as well as administrators, attendings, chief residents, administrative residents, and head PAs, and request names of potential participants for Aims 1 and 2. We will email the identified providers, mentioning the person who recommended that they might be interested in participating, and asking if they would like to participate in our study. Alternatively, we will ask department heads, administrators, or other faculty or staff to email potential participants and inform them of our study. We may also present our study at ED faculty meetings and/or resident meetings to raise awareness of our study. Alternatively, we will ask department heads, administrators, or other faculty or staff to present our study in information sessions to promote participation.

For AIM 2, eligibility and recruitment methods will be the same as for AIM 1, as indicated in the previous paragraph. We will contact participants using the health system email. We may also ask department heads, administrators, or other faculty or staff to distribute and/or display flyers to promote our study. The flyer may also be distributed through the physician Teams chat. We will inform potential participants and solicit interest, offering a \$50 reimbursement for their time. There may be one follow-up phone call.

For AIM 3, full time ED providers will be eligible. We will conduct a pilot trial of PERK among 150 Emergency Medicine providers at NSUH and LIJMC. We expect 150 providers who meet the inclusion criteria to be in each of the pre- and post-groups.

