In AIM 3, we will conduct a pilot trial to evaluate the feasibility, acceptability, and preliminary efficacy on provider adoption of the new tool, “PERK”, compared to the current PE CALC tool. This will consist of a six month prospective cohort pilot study with a retrospective cohort control group. All full time ED providers at NSUH and LIJMC will be eligible for participation. Training on PERK use will be conducted as a presentation during ED Grand Rounds. This will be led by [name] and a research coordinator. It will last about 30 minutes with three basic components: 1) overview of the evidence supporting tool use, 2) hands-on session to practice using the tool, and 3) question and answer session. Similar educational training was conducted before launching the current tool, PE CALC.

For the pilot study, we will use EHR reporting data to generate a PERK monitoring dashboard. The dashboard will include trigger rates (percentage of ED patients for which the tool triggers), adoption rates (the percentage of times the provider completes the calculator once the tool is triggered), CTPA order rates (percentage of total ED patients for which a CTPA is ordered for the evaluation of PE), and CTPA yield (the percentage of tests ordered to evaluate for PE that are positive for PE).

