For AIM 3, we will determine the feasibility of PERK using post-pilot provider satisfaction surveys, where mean scores for each response on a Likert scale will be reported with standard deviations and 95% confidence intervals. Acceptability will be determined from post-pilot stakeholder interviews with providers, nurses and the ED chairs at both institutions. Preliminary efficacy will be assessed by comparing provider adoption of PERK to provider adoption for the first six months of PE CALC. Providers in the pre- and post- groups will be summarized using descriptive statistics. Provider age, gender, race and type (attending vs. resident vs. physician assistant) will be compared between the two groups using two-sample t-test or Wilcoxon Rank Sum test for continuous variables and Chi-squared or Fisher's exact test for categorical variables. Since the variability of the adoption rate of PERK for each provider depends, in part, on the number of encounters, providers with larger numbers of encounters should carry more weight. Therefore, a weighted two-sample t-test will be used to test the difference in the weighted means of adoption rates between the groups. Weighted least squares linear regression with number of encounters as weight for each observation (provider) will be performed, to see whether there is difference in the adoption rate between the two groups after controlling for provider age, gender, race, type and other confounding variables.

Power Calculations: We expect 150 providers who meet the inclusion criteria to be in each of pre- and post- groups. We also assume the mean adoption rate of the pre group to be 15% with the standard deviation of 10% based on the historical data, and the mean adoption rate of the post- group to be 20%, 25% and 30% with equal standard deviation. With the sample size of 150 in each group, there will be at least 99% power to detect the difference of 5%, 10% and 15% in the mean adoption rates using a two-sided two-sample t-test at a significance level of 0.05. We are aware that the weighted two-sample t-test should be used to calculate the power. However, due to the lack of information about weights, the unweighted two-sample t-test was used instead.

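### The adoption hypothesis (H2) rests by default on an unadjusted weighted t-test in a non-randomised comparison; the planned covariate-adjusted regression should be named as the deciding analysis

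*Combined protocol and SAP*

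**What the plan says.** Section 4 makes provider adoption the primary efficacy outcome of Aim 3. H2 is that PERK "will demonstrate higher provider adoption as compared to PE CALC". Section 11 describes a "six month prospective cohort pilot study with a retrospective cohort control group", and Section 4 places the control data in an earlier period, "comparing it to retrospective data from the first 6 months of PE CALC".

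Section 12 sets out three steps for adoption:

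- The two groups are compared on provider age, gender, race and type (attending, resident or physician assistant).
- Then "a weighted two-sample t-test will be used to test the difference in the weighted means of adoption rates between the groups". This test has no covariates.
- "Weighted least squares linear regression with number of encounters as weight for each observation (provider) will be performed", to look for a group difference "after controlling for provider age, gender, race, type and other confounding variables". The further confounders are not listed.

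The power paragraph in the same section accepts that the weighted t-test is the proper basis for power. It substitutes the unweighted version because nothing is known about the weights. No power is given for the regression. Neither analysis is called primary, secondary or supportive, and no rule covers disagreement between them.

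**The concern.** The groups are defined by calendar period, so nothing in the design balances provider characteristics. Section 12 recognises this far enough to plan an adjusted model. Yet the analysis worded as the test of the adoption difference, and the one that power refers to, takes no account of those characteristics.

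Provider type is the obvious route for bias. Section 6 says of eligibility: "This includes residents in the Emergency Medicine/Internal Medicine program". Residents, attendings and physician assistants may use a decision tool at different rates. Because providers are weighted by encounters, what counts is the mix of encounters by provider type, and that can move between periods even when headcounts do not.

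Two things are at stake. First, a significant t-test could reflect provider mix instead of PERK. Second, two analyses address one hypothesis, one of them with an open covariate list. If they disagree, the plan does not say which result stands, so the choice could be made after the results are seen.

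**Working it through.** **Inputs from Section 12.** 150 providers per group; SD of adoption 10 points in both groups; pre-group mean 15%; differences of 5, 10 and 15 points; two-sided alpha 0.05.

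**1. The plan's own figure.**
- SE = 10 × √(2/150) = 1.155 points.
- Power for 5 points = Φ(5/1.155 − 1.96) = Φ(2.37) = 99.1% (also 99.1% with the noncentral t, 298 degrees of freedom).
- Power for 10 and 15 points exceeds 99.9%.

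The stated figure of at least 99% reproduces. It belongs to the unadjusted, unweighted test.

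**2. Rejection by the unadjusted test when PERK has no effect.**
- Shift b = (difference between periods in one provider type's share) × (adoption gap between that type and the others).
- Rejection probability = P(Z > 1.96 − b/SE) + P(Z < −1.96 − b/SE).

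The documents give neither factor of b, so these values are assumed:
- 10-point change in share × 10-point gap: b = 0.10 × 10 = 1.0 point.
- 10-point change in share × 15-point gap: b = 0.10 × 15 = 1.5 points.

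The SE in step 1 ignores the weights. Uneven encounter counts enlarge it by √(design effect), and the design effect is also assumed.

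| Weighting design effect | SE (points) | b = 0 | b = 1.0 | b = 1.5 |
|---|---|---|---|---|
| 1 (unweighted) | 1.155 | 5.0% | 13.9% | 25.5% |
| 1.5 | 1.414 | 5.0% | 10.9% | 18.5% |
| 2 | 1.633 | 5.0% | 9.4% | 15.1% |

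For example, with b = 1.0 and no weighting loss, b/SE = 0.866, giving P(Z > 1.094) + P(Z < −2.826) = 0.137 + 0.002 = 0.139.

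**3. What the adjusted model costs in power.** Let R² be the share of variation in group membership explained by the covariates. The SE is divided by √(1 − R²). Conservatively, assume the covariates explain none of the variation in adoption. Power for 5 points is then Φ(5/SE − 1.96):

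| Weighting design effect | R² = 0.1 | R² = 0.2 | R² = 0.3 |
|---|---|---|---|
| 1 | 98.4% | 97.2% | 95.2% |
| 1.5 | 91.8% | 88.5% | 84.1% |
| 2 | 82.8% | 78.2% | 72.6% |

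Much of this loss comes from weighting, which the weighted t-test would bear too. Its own power at a design effect of 2 is 86.5%.

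**The case against.** A reader might infer that the plan makes the t-test the formal decision rule and treats the regression as a mere follow-up look. The documents do not support that. The regression is firmly planned, uses the encounter weights, asks the same question and is nowhere labelled secondary. The t-test's priority is a default reading, from its wording as the test and from the power paragraph. This part of the objection stands: the defect is that no deciding analysis is named, not that an adjusted analysis is missing.

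A reader might also infer that the adjusted model would be unbiased. That too goes beyond the documents. Group and calendar period coincide, so no covariate adjustment can separate PERK from other changes over time. The model addresses only measured, correctly modelled provider characteristics.

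The illustration is open to fair challenge. Its shifts are assumed, and they are small beside the 5 to 15 points in the power paragraph. Its SE treats the groups as independent, although both come from the same two departments (86 + 63 = 149 eligible, Section 5). Many providers may be in both groups. Overlap would tend to limit imbalance in gender, race and type, and positive within-provider correlation could lower the rejection rates further. The documents do not give the overlap, and neither analysis addresses the pairing. Comparing groups on provider characteristics is also routine and is no evidence that they will differ, and the eligibility of residents shows no change in their share.

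Finally, Aim 3 is a pilot of preliminary efficacy, which limits the seriousness of the point. It does not remove it: H2 is a stated hypothesis with a planned test and power at two-sided 0.05.

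**Conclusion.** The point holds as a cheap improvement. In a non-randomised pre-post comparison, the analysis worded as the test of adoption is unadjusted, and the adjusted regression already planned is not designated as deciding H2. Followed as written, the t-test can reject because of provider mix alone.

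The size is not known. Under the assumed shifts, false rejection is about two to five times the nominal 5% without weighting loss, and about two to three times at a design effect of 2. These figures rest on an assumed change in mix, an assumed adoption gap by provider type and independent groups. They show that modest imbalance would be enough, not that it will occur. The stated power is arithmetically correct and is not evidence for the concern.

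**What to change.** In Section 12:

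- State that H2 is judged by the period coefficient and its 95% CI from the planned encounter-weighted regression.
- Replace the open reference to other confounders with a full covariate list, fixed before PERK data are extracted.
- Report the unadjusted weighted t-test as descriptive.
- State that adjustment covers measured provider characteristics only and cannot remove calendar-period effects.
- State that the 99% power figure applies to the unadjusted, unweighted test.

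The cost is a few sentences and the work of settling the covariate list; the model itself is already planned. Some precision is lost: under the assumed ranges, power for 5 points stays at about 84% to 98% for design effects up to 1.5, and falls to about 73% to 83% at a design effect of 2. The unadjusted result can no longer be the headline.

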11. RESEARCH PROCEDURES

- *Include a detailed description of all procedures to be performed on the research subject and the schedule for each procedure.*
- *Include any screening procedures for eligibility and/or baseline diagnostic tests*
- *Include procedures being performed to monitor subjects for safety or minimize risks*
- *Include information about drug washout periods*
- *If drugs or biologics are being administered provide information on dosing and route of administration*
- *Clearly indicate which procedures are only being conducted for research purposes.*
- *If any specimens will be used for this research, explain whether they are being collected specifically for research purposes.*
- *Describe any source records that will be used to collect data about subjects*
- *Indicate the data to be collected, including long term follow-up*

In AIM1, we will conduct semi-structured interviews with low, intermediate, and high users of the current tool, PE CALC (n=12 total, 4 each, continuing until data saturation) to refine our understanding of barriers to tool use and receive feedback on nudges' acceptability and ability to address identified barriers. Guided by our preliminary survey data and the COM-B framework, we will develop an interview guide. The interview will have three goals: 1) refinement of the four most prevalent barriers, 2) assessment of how well each nudge addresses the behavioral barrier, and 3) acceptability of the nudge. [name] will conduct structured interviews at NSUH, LIJMC, [name], and other clinical sites including [name] with [name], PhD, an experienced researcher. The interviews will be audio recorded (using two digital voice recorders; one for backup in case of technical failure) and professionally transcribed. The guide will be revised based on the ongoing analysis of interview data.

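### Encounter-weighted t-test and WLS for H2: the usual model-based standard errors need variance proportional to 1/encounters and independent pre and post groups, and the plan assures neither

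*Combined protocol and SAP*

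**What the plan says.** Section 12 (Aim 3) argues that a provider's adoption rate is more precise when it rests on more encounters, while conceding that encounters explain only part of its variability. From this it derives the test of H2: "a weighted two-sample t-test will be used to test the difference in the weighted means of adoption rates between the groups". The adjusted analysis follows: "Weighted least squares linear regression with number of encounters as weight for each observation (provider) will be performed". No variance formula is given for the weighted t-test. No robust variance, overdispersion term or provider effect is named for either analysis.

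The power paragraph assumes "the mean adoption rate of the pre group to be 15% with the standard deviation of 10% based on the historical data", states "We expect 150 providers who meet the inclusion criteria to be in each of pre- and post- groups", and calculates power "using a two-sided two-sample t-test at a significance level of 0.05". It uses the unweighted test because nothing was known about the weights. No section gives the mean or spread of encounters per provider.

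Four other places bear on the variance:
- Section 11 plans "semi-structured interviews with low, intermediate, and high users of the current tool, PE CALC".
- Section 3 reports that 15% of providers used PE CALC, which was implemented at the same two emergency departments.
- Section 5 counts 86 + 63 = 149 eligible providers at those departments.
- Section 11 sets a prospective cohort against a retrospective one. The plan does not say how a provider who appears in both is handled.

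**The concern.** Weighting each provider by n_i encounters and using the standard WLS variance amounts to assuming Var(rate_i) = φ/n_i. If providers also differ in their true adoption rates, part of the variance does not shrink as n_i grows. The model-based standard error is then too small wherever encounters vary between providers. That they vary is the plan's own reason for weighting.

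A second assumption is independence between the groups. A provider who contributes to both periods brings positive covariance, which lowers the true variance of the difference. A two-sample analysis ignores this, so its standard error is then too large.

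These are the only inferences planned for the primary efficacy outcome. The two errors act in opposite directions and nothing makes them cancel, so the stated 5% level and the confidence interval are not assured. As this is a pilot, the interval and its standard error are also likely to inform later studies.

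**Working it through.** **Inputs from section 12.** Two-sided 5% level; 150 providers per group; mean 15% and SD 10% in the pre group; post-group means of 20%, 25% and 30% with the same SD. **Assumed, because the documents are silent:** mean encounters per provider (10 to 100), their coefficient of variation (CV, 0.3 to 1.0), and the degree of provider overlap.

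**1. The plan's own figure.** For a 5-point difference, SE = 0.10 × √(2/150) = 0.01155, so the difference is 0.05/0.01155 = 4.33 standard errors. The noncentral t with 298 df gives power 99.1%, which reproduces the stated figure of at least 99%.

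**2. What mean 15% and SD 10% say about provider differences.** Binomial noise alone has variance 0.15 × 0.85/n. It equals 0.10² at n = 0.1275/0.01 = 12.75 encounters. With equal encounters, the share of variance left for true provider differences is 1 − (0.1275/n)/0.01:

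| Encounters per provider | Between-provider share |
|---|---|
| about 13 or fewer | 0% |
| 20 | 36% |
| 30 | 57% |
| 50 | 75% |
| 100 | 87% |

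**3. Limiting case, independent groups.** Suppose all the variance σ² lies between providers and the weights are n_i.
- True variance of a weighted mean: σ²Σn_i²/(Σn_i)² = σ²(1 + CV²)/N.
- Model-based WLS variance: about σ²/N.
- The ratio is 1 + CV², so the true error rate is 2[1 − Φ(1.96/√(1 + CV²))]. This is 8.0%, 11.7% and 16.6% at CV 0.5, 0.75 and 1.0.

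**4. Simulation under no effect, independent groups.** Beta-binomial providers, 150 per group, mean 15%, lognormal encounters, 8,000 runs per cell (Monte Carlo SE about 0.24 points at 5%). The total SD was held at 10% where attainable. Binomial noise alone exceeds 10% at mean 10, at mean 15 with CV 0.5 or more, and at mean 20 with CV 1.0; there the provider component was set to almost nil. Rejection rates of the nominal 5% WLS test with model-based SE:

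| Mean encounters | CV 0.3 | CV 0.5 | CV 0.75 | CV 1.0 |
|---|---|---|---|---|
| 10 | 5.0% | 5.5% | 4.8% | 5.0% |
| 15 | 5.1% | 4.9% | 4.7% | 5.3% |
| 20 | 5.5% | 5.3% | 5.4% | 5.1% |
| 30 | 5.7% | 6.1% | 7.9% | 8.4% |
| 50 | 5.9% | 7.4% | 9.8% | 12.6% |
| 100 | 6.1% | 7.2% | 11.0% | 14.2% |

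In the worst cell the true SE is 1.35 times the reported one. With the same weights and an HC3 robust variance, the error rate was 4.6-5.4% in every cell.

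**5. Same providers in both periods.** Eighteen scenarios were run: mean 30 with CV 0.5 or 1.0, and mean 50 with CV 0.75, each with 50-100% overlap and a 30-70% chance that an overlapping provider keeps the same true rate. Model-based WLS ran at 1.1-7.1%, and its SE was too large in 11 of the 18. HC3 without clustering ran at 0.4-4.3%. In a separate set of runs, a variance clustered by provider held 4.8-5.6%.

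**The case against.** The strongest reply is that the size, and even the direction, of the error is unknown.

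- **The plan's figures do not prove provider differences.** A reader might infer from the 15% mean and 10% SD that providers truly differ. They do not show this, because about 13 encounters per provider produce that SD by chance alone. This stands.
- **The other evidence is qualitative.** Levels of use may be raw counts (section 6 identifies interviewees by PE CALC use), and observed use can be ranked even under one common rate. The 15% of providers in section 3 may be the same figure that section 12 uses as a mean rate. Together with section 12's own concession about encounters, these make a single common rate doubtful, but they do not size the spread. This stands.
- **The standard error need not be too small.** A reader might also infer that it must be. That requires independent groups. With 149 eligible providers at the same two departments, overlap is plausible and can make the test conservative. This stands, but overlap is a second unmodelled feature and not a safeguard.
- **The weighted t-test has no stated formula.** With a linearised variance the inflation in step 4 would not arise. So the point is firm for standard WLS and conditional for the t-test.
- **Weighting is defensible.** Section 11 defines adoption as the share of triggers completed, and an encounter-weighted mean targets this directly. The point estimates need not change.
- **The planned effects are large.** At 5 points, multiplying the SE by √2 (the CV 1.0 limit) still leaves 4.33/1.414 = 3.1 standard errors. The conclusion would change only for effects well below those planned. This limits the consequence, but it does not make the interval correct.

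**Conclusion.** The point holds in conditional form. Run with the usual model-based standard errors, the two planned analyses of H2 rest on a variance model that section 12 itself only partly endorses, and on an independence that the design does not secure.

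For independent groups with a total SD of 10%, the nominal 5% test runs at about 5-14%. Inflation is negligible at about 20 or fewer encounters per provider and at most about one point at CV 0.3. Reaching 7% needs roughly 30 or more encounters with a CV of about 0.5-1.0 (at a mean of 30, about 0.75 or more). With overlapping providers the test can instead be conservative. All of this rests on assumed encounter counts and assumed overlap. The documents do not support a claim that the standard error is certainly too small, nor one fixed figure for the inflation.

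Severity: should be fixed before the analysis. It is not a fatal flaw in a pilot of preliminary efficacy.

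**What to change.** In section 12 (Aim 3):

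1. Keep the encounter-weighted means and the WLS point estimates. Take every standard error, confidence interval and p-value from a robust variance clustered by provider, with one provider ID spanning both periods. Plain HC3 is not enough if providers overlap.
2. Alternatively, model completions out of triggers with a mixed logistic regression and a provider random effect spanning both periods. State that this changes the estimand, from a difference in encounter-weighted rates to an odds ratio conditional on provider.
3. State the variance formula for the weighted t-test, or obtain that test from the regression in item 1 without covariates.
4. Report the distribution of encounters per provider in each period (mean and CV at least) and the number of providers present in both.

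**Cost.** Wording and a few lines of code on the same data. A coded provider ID must be kept for both periods. Section 24 describes the EHR data as de-identified and aggregate, so this should be reconciled with the provider-level records that the planned regression already needs. The confidence interval may widen if providers truly differ; with substantial overlap it may narrow.

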2. BRIEF SUMMARY OF RESEARCH

- *The summary should be written in language intelligible to a moderately educated, non-scientific layperson.*
- *It should contain a clear statement of the rationale and hypothesis of your study, a concise description of the methodology, with an emphasis on what will happen to the subjects, and a discussion of the results.*
- *This section should be ½ page*

United States citizens receive only half of recommended medical care¹ and a third of the care received is unnecessary². The disparity between usual and evidence based clinical practice is responsible for a third of hospital deaths³ and waste estimated at 380 billion dollars each year⁴. Computerized clinical decision support (CDS) attempts to close the gap by bringing meaningful and relevant evidence to health care providers at the point of decision making. Providers, policymakers, experts and consumers have identified these as key tools to revolutionize health care.⁵⁻⁷ However, the moderate improvements in care seen with CDS⁸⁻¹⁴ have been significantly limited by consistently low provider adoption, estimated at 10%^{15,16}. Thus, there is a critical need to identify strategies to increase provider adoption of CDS.

The central hypothesis of this proposal is that the addition of a theory-informed “nudge” to a CDS tool will address identified behavioral barriers to use and significantly improve adoption by providers. Nudges are applications of behavioral science, defined as positive reinforcement and indirect suggestions that have a non-forced effect on decision making¹⁷. For example, default options for organ donation consent lead to striking differences in enrollment.¹⁸ Previous studies on the impact of nudges on provider behavior have demonstrated exceptional results (i.e. decreased inappropriate antibiotic prescribing from 20% to 4%¹⁹) but have not examined their impact on provider adoption of CDS. We propose to use a behavioral theory-informed process to develop a new CDS tool that includes a nudge that addresses barriers to adoption.

We designed a CDS tool (**PE CALC**) to reduce unnecessary computed tomography pulmonary angiography (CTPA) testing for pulmonary embolus (PE) that is efficacious (37% reduction among tool adopters) when used. However, its overall impact is limited by low provider adoption (15%). Users identified low *social opportunity* [“my colleagues don’t use the tool”], *reflective motivation* [“good

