3. INTRODUCTION/BACKGROUND MATERIAL/PRELIMINARY STUDIES AND SIGNIFICANCE

- *Describe and provide the results of previous work by yourself or others, including animal studies, laboratory studies, pilot studies, pre-clinical and/or clinical studies involving the compound or device to be studied.*
- *Include information as to why you are conducting the study and how the study differs from what has been previously researched, including what the knowledge gaps are.*
- *Describe the importance of the knowledge expected to result*

Clinical decision support (CDS) has been shown to improve quality of care. Meta-analyses of the effect of CDS have shown that providers who use decision support are more likely to order appropriate treatments and provide preventive care services.^{8,21-23} Extensive study of these tools has shown a morbidity decrease of 10 to 18%, placing CDS at the top of the spectrum of quality improvement interventions.²⁴ The expectation of CDS to improve the practice of medicine was communicated with the unprecedented federal resources (\$30 billion) committed to supporting the use of EHRs through the HITECH Act of 2009, where "meaningful use" requirements demand the use of CDS.²⁵ These tools have great potential to improve quality of care.

In spite of the clear benefits of using CDS, meta-analyses have found provider adoption of these tools to be low²⁶ with up to 96% of CDS being overridden²⁷. There is clear evidence of providers not using well thought out CDS, undermining potential clinical impact.²⁸ A systematic review of randomized controlled trials of CDS impact, found four system features to be independently predictive of successful clinical practice improvement.²⁹ Each of these factors improve provider

adoption (automatic triggering, including specific recommendations, workflow integration and computer based support). Improving provider adoption of CDS can help these tools reach their potential to improve quality of care.

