Each CTPA carries a 14% risk of contrast induced nephropathy³⁸ and a lifetime malignancy risk that can be as high as 2.76%³⁹. Incidental findings requiring diagnostic follow up are found in 24% of tests, increasing both costs and harms from repeat imaging.⁴⁰ The use of clinical prediction rules to assess pre-test probability before CTPA reduces testing by 25% without any missed PEs.^{41,42} Their routine use by providers would result in 600,000 fewer scans, 84,000 fewer cases of contrast induced nephropathy and prevent 3,000 malignancies as well as 2,000 cancer deaths in the United States every year³⁹.

We based PE CALC on provider preferences, using a well-validated clinical prediction rule perceived as “most useful” by providers surveyed at Northwell Health (the Well’s Score for PE). We implemented this tool in the EDs of NSUH and LIJMC and found that the tool was efficacious when used, with an increase in CTPA yield from 8% to 12% (a 37% reduction in unnecessary CTPAs) among adopters. However, it did not increase CTPA yield for the ED as a whole, as it was only used by 15% of providers. The goal of this study is to add nudges to PE CALC to develop a new tool, which we will call Pulmonary Embolism Risk Kalculator, or PERK. To our knowledge, our study will be the first to use behavioral theory to illuminate the impact of nudges on provider adoption of CDS. We hope that the results of our study will include not only a new CDS tool with higher adoption rate and efficacy than our previous PE CALC, but also new insight into the effects of nudges on provider adoption of CDS tools.

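### Does the background statement that 15% of providers used PE CALC undermine the 15% mean and 10% SD behind the power calculation?

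*Combined protocol and SAP*

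**What the plan says.** All places are in the combined protocol and SAP.

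- **Section 12, Power Calculations:** "We also assume the mean adoption rate of the pre group to be 15% with the standard deviation of 10% based on the historical data". Post-group means are 20%, 25% and 30% with the same SD, there are 150 providers per group, and the test is a two-sided unweighted t-test at 0.05. The conclusion is "there will be at least 99% power to detect the difference of 5%, 10% and 15% in the mean adoption rates".
- **Section 11, Aim 3 dashboard:** the adoption rate is "the percentage of times the provider completes the calculator once the tool is triggered". This is a share of triggers.
- **Section 3, PE CALC results:** the tool did not raise yield for the department as a whole because "it was only used by 15% of providers". This is a share of people.
- **Sections 2 and 4:** both give the 15% as low provider adoption and state no unit.
- **Section 3, general background:** low adoption is illustrated by "up to 96% of CDS being overridden", which counts alerts, not people.
- **Section 4, Aim 3:** PERK is evaluated by "comparing it to retrospective data from the first 6 months of PE CALC".

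**The concern.** The same 15% appears with two units. Suppose 15% of providers used the tool and the other 85% never did. The mean completion rate could then reach 15% only if every user completed the calculator at every trigger, and the SD would be about 36%, not 10%. The baseline mean and SD would have been built on a misread historical figure. Adoption is the study's endpoint and this 15% is its only stated baseline. The 5-point power claim also has almost no slack, so a larger true SD would break it.

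**Working it through.** **Inputs.** Mean 15%, SD 10%, 150 per group, differences of 5, 10 and 15 points, two-sided 0.05 (Section 12); 15% of providers (Section 3); 86 + 63 = 149 eligible providers (Section 5).

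**1. The plan's own power.** The standard error of the difference is 0.10 × √(2/150) = 0.01155. At 5 points the noncentrality is 0.05/0.01155 = 4.33. The normal approximation gives Φ(4.33 − 1.96) = Φ(2.37) = 99.1%, and the noncentral t also gives 99.1%. At 10 and 15 points power exceeds 99.9%. The stated figure reproduces. At 5 points, 99% power needs an SD of no more than 10.07%, and 80% power needs an SD of no more than 15.4%.

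**2. How many providers must have some use.** If a share p is non-zero and the overall mean is m, then SD² ≥ m²(1/p − 1). With m = 0.15 and SD = 0.10, p ≥ 0.0225/(0.0225 + 0.0100) = 0.692, or 104 of 150. Section 3 read literally gives 0.15 × 149, or about 22 providers.

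**3. The same check for any threshold of use.** Split providers into 15% with mean a and 85% with mean b. The between-group variance cannot exceed the total:

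- 0.15 × 0.85 × (a − b)² ≤ 0.10², so a − b ≤ 0.10/√0.1275 = 0.280.
- 0.15 = b + 0.15(a − b), so b ≥ 0.15 − 0.042 = 0.108.

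The 85% not counted as users would therefore average at least 10.8%, whatever cut-off defines use. Both bounds treat the mean and SD as unweighted, as the power calculation does.

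**4. If the 15% really were a head count.** Let users complete the tool on a share u of triggers and everyone else on none. The mean is 0.15u and the SD is at least u√(0.15 × 0.85) = 0.357u. Section 12's t-test with 150 per group, and that minimum SD in both groups, gives:

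| u (assumed) | Mean | Minimum SD | Power at 5 points | Power at 10 points | Power at 15 points |
|---|---|---|---|---|---|
| 25% | 3.75% | 8.9% | 99.8% | >99.9% | >99.9% |
| 50% | 7.5% | 17.9% | 68% | 99.8% | >99.9% |
| 75% | 11.25% | 26.8% | 36% | 90% | 99.8% |
| 100% | 15% | 35.7% | 23% | 68% | 95% |

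The documents do not give u. Spread among users would raise these SDs: at u = 25% with an SD of 10% among users, 5-point power is 99.3%, and with 15% it is 98.2%. The head-count reading does not settle the power in either direction.

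**The case for a change.** The best case for acting is that Section 3 reads naturally as a head count. It reports a benefit among adopters and explains the absent department-wide effect by how few providers used the tool. Nothing in the documents reconciles the units or says who counts as a user. The bounds in steps 2 and 3 assume no distribution shape. The check would also be cheap, since Section 6 says "potential subjects will be identified using the Electronic Medical Records (EMR) based on PE CALC use". If adoption were compared as a share of providers (15% against 20%, 25% and 30%), power would be about 21%, 59% and 88%.

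The mismatch and the bounds stand, and so does the thin margin at 5 points. What does not follow is that the power statement is wrong. The 21%, 59% and 88% belong to an endpoint the plan does not use, and the 23% figure needs every user to complete the tool at every trigger. The conflict itself also has limits. Section 3 names no period. Section 11 sorts current users into three levels for the Aim 1 interviews, so use is treated as graded. Section 2 puts typical decision-support adoption at 10% and calls it low, so a group averaging 10.8% could loosely be described as not having adopted the tool.

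**Conclusion.** This is a slip of wording in background text, and it calls for no change to the plan. The likeliest reading is that the Section 3 clause loosely restates a 15% completion rate. Section 11 defines adoption per trigger, Section 3 itself describes low adoption through overrides, and Section 12 carries the 15% as a mean rate with its own SD, attributed to historical data. On that reading the Section 12 inputs are in the right unit and the 99.1% at 5 points holds. A second possibility is an unstated threshold for counting someone as a user, which also leaves Section 12 intact.

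Little turns on the choice. The efficacy comparison uses observed PE CALC data, so the 15% does not enter the analysis. Enrolment takes in all eligible full-time providers and does not depend on the power figure. Analysts working from the Section 11 definition will compute the pre-group rate in the correct unit whatever the background clause says.

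This conclusion assumes that the Section 12 mean and SD came from per-provider completion rates, as the text indicates. The historical data are not in the documents, so that cannot be confirmed here. If the 15% proved to be a head count, the planning mean would be wrong unless users completed the tool at every trigger, and 5-point power would lie between about 99.8% (users at 25% of triggers) and 23% (users at 100%), at the minimum SD in each case. Nothing in the documents shows that to be so.
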